7.2.2.7. SF36 physical and mental scores

The SF-36 physical score corresponds to the SF-36 physical component summary and the SF-36 mental score corresponds to the SF-36 mental component summary which are calculated according to the user’s manual for the SF-36v2 health survey – third edition, using a dedicated software and transferred in the ClinTrial database.

7.2.2.8. Schirmer test

The Schirmer test determines whether the eye produces enough tears to stay moist. This test results in a measure of the moisture on paper strips previously applied on eyes for five minutes. The results of the Schirmer test will be directly available in ClinTrial. The mean score of both eyes will be derived as the mean of right eye and left eye. The score will be evaluated on the mean of both eyes but also the most affected eye which means on the eye with the smallest score at baseline. If both eyes have the same Schirmer score at baseline, the right eye will be evaluated by default.

7.2.2.9. OSS

The Ocular Staining Score (OSS) uses lissamine green dye to grade the conjunctiva and fluorescein dye to grade the cornea. Total ocular staining scores of 0 to 12 *per* eye assess the range of severity of keratoconjunctivitis sicca.

The total OSS for each eye is the summation of the fluorescein score for the cornea and the lissamine green scores for the nasal and temporal bulbar conjunctiva. The maximum possible score for each eye is 12. The mean score of both eyes will be derived as the mean of right eye and left eye. The score will be evaluated on the mean of both eyes but also the most affected eye which means on the eye with the highest score at baseline. If both eyes have the same OSS score at baseline, the right eye will be evaluated by default.

7.2.2.10. Sialometry under unstimulated and stimulated conditions

The results of the sialometry tests will be available in ClinTrial and the flow rate of saliva automatically calculated as Volume (mL)/minute.

7.2.3. Safety

7.2.3.1. Adverse events

Each **medical concept of adverse event coded according to the internal "multiple medical concept" process** is taken into account as a single adverse event in the statistical analysis. The modalities of the adverse event (onset and end dates, intensity, seriousness, action taken, additional therapy, relationship, outcome...) replicated by default to each medical concept are also taken into account in the statistical analyses.

Treatment Emergent Adverse Events (TEAE) are defined in [Section 4.4.1](#).

Serious adverse events are defined as all adverse events upgraded by the sponsor during the IME or Pharmacovigilance (PV) process (upgrade of seriousness) or considered as "serious" from investigator assessment.

Serious adverse events from investigator assessment are defined as all adverse events fulfilling at least one of the following seriousness criteria for immediate notification at any time (before, during or after IMP intake): death, hospitalisation or prolongation of hospitalisation, medically important, life-threatening, disability/incapacity or congenital anomaly.

Severe adverse events are defined as adverse events of grade 3, 4 or 5.

A fatal adverse event corresponds to an adverse event with "Fatal" outcome.

Adverse events of special interest (AEOSI) are adverse events of scientific and medical interest or concern regarding the IMP for which recording rules, special documentation with detailed information such as hospital records is required. It may be a serious or non-serious AE that may require further investigation in order to characterize and understand.

AEOSI include:

- Allergic reaction grade 3 or higher according to CTCAE/v5.0 grading (Note: Humans administered foreign proteins are at risk of developing allergic reactions, including anaphylaxis).
- Cytokine release syndrome: No cytokine release has been observed in FIH study (IFN γ , IL12p70, IL4, IL5, IL6, IL8, TNF α , however, given the risk of cytokine release syndrome observed in certain therapeutic monoclonal antibodies, this event will be systematically collected and closely monitored in patients treated with S95011). In case of suspicion of cytokine release syndrome, a blood sample for cytokines assay will be performed and analysed locally.
- Infections grade 3 or higher according to CTCAE/v5.0 grading (Note: IL 7 receptor inhibition may induce immunomodulation, so patients should be monitored clinically for manifestations of infectious disease, and, if necessary, appropriately treated [e.g. with antibiotics]).
- Lymphopenia < 500x10⁶/L (grade 3 or higher according to CTCAE v5.0 Criteria)

The lists of the considered ATC codes for AEOSI are the excel files:

- 3736.0 PRE Infusion related reaction M251.
- 3847.0 Lymphopenia M250.
- 4314.0 Bacterial, viral, fungal, parasitic infections for 95011 M250.
- 4639.0 Cytokine release syndrome M250.

Adverse events related to IMP correspond to adverse events with relationship with IMP forced by the sponsor during the PV process (upgrade of relationship at least for adverse events assessed as serious according to investigator or sponsor opinion) or considered as "related" from investigator assessment.

The following information will be taken into account:

- For the analyses where the intensity of the adverse event is considered, the worst intensity from the day of emergence to the end of the studied period will be taken into account.
- For the analyses where the action taken regarding the IMP is considered, all the actions taken recorded from the day of emergence to the end of the studied period will be taken into account.
- For the analysis of recovered emergent adverse events during, an EAE is considered as recovered "during treatment period" if the associated outcome is "recovered" or "recovered with sequelae" and occurs between the first IMP intake date and the last IMP intake date.

CL2-95011-001 - Statistical Analysis Plan | VV-TMF-116033 | 2.0

The following rules are applied in case of missing intensity to define emergent adverse events:

Table (7.2.3.1) 1 - Adverse events - Rules in case of missing intensity

Intensity			Worsening of intensity
Nearest before the first IMP intake date	During studied period*		
Missing	Missing	⇒	Yes
Missing	Grade 1	⇒	No
Missing	Grade 2	⇒	Yes
Missing	Grade 3	⇒	Yes
Missing	Grade 4	⇒	Yes
Missing	Grade 5	⇒	Yes
Grade 1	Missing	⇒	Yes
Grade 2	Missing	⇒	Yes
Grade 3	Missing	⇒	Yes
Grade 4	Missing	⇒	Yes
Grade 5	Missing	⇒	No

* Studied period – cf Section 4.4.1

The rules for substitution of missing or incomplete onset date, dates of modification of intensity, dates of action taken and/or dates of the six seriousness criteria are as follows:

Table (7.2.3.1) 2 - Substitution rules of AE dates

Date to substitute	Substituted date
dd/mmm/yyyyhh: ..	If same date and same hour as IMP intake date then: - First intake date and time + 1 min Else: hh:00
dd/mmm/yyyy ...-...	If same date as IMP intake date then: - First IMP intake date and time + 1 min Else: - dd/mmm/yyyy 00:00
../mmm/yyyy.....	If same month and year as IMP intake date then: First IMP intake date and time + 1 min Else: 01/mmm/yyyy 00:00
../.../yyyy ...:	If same year as IMP intake date then: First IMP intake date + 1 min Else: 01/JAN/yyyy 00:00
../.../.....	First IMP intake date and time + 1 min

Note: ../mm/yyyy = missing day
../.../yyyy = missing day and month
../.../... = missing date
dd/mmm/yyyyhh: .. = missing minutes
dd/mmm/yyyy: ... = missing time

CL2-95011-001 - Statistical Analysis Plan | VV-TMF-116033 | 2.0

The rules for substitution of missing or incomplete recovery dates, in case of AE outcome "recovered" or "recovered with sequelae" are as follows:

Table (7.2.3.1) 3 - Substitution rules of recovery date

Date to substitute	Substituted date
../mmm/yyyy	If same month and year than date of AE last information* then: Date of AE last information Else: Last day of the month /mmm/yyyy
../.../yyyy	If same year than date of AE last information* then: Date of AE last information Else: 31/DEC/yyyy
../.../....	Date of AE last information*

* Date of AE last information is defined as the maximum between onset date, dates of modification of intensity, action taken and dates of the six seriousness criteria for this adverse event.

Note:

../mmm/yyyy = missing day,
../.../yyyy = missing day and month,
../.../.... = missing date.

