Five studies have been conducted with GSK 26118960 and PF 06342674 in around 150 people including at least 98 healthy volunteers with administered single or multiple weekly doses from 0.25 mg/kg to 6 mg/kg IV or SC. Two of these studies (Ellis *et al*, 2018; Herold *et al*, 2019) have been published and partial results from the other studies can be found on <https://clinicaltrials.gov>. (NCT01808482; NCT02293161; NCT01740609; NCT02045732; NCT02038764). No significant adverse event nor adverse drug reaction has been described within the available information.

Up to now, no safety issue in the phase 1 study in healthy volunteers was reported with S95011. However, due to its nature, IV administration and mechanism of action, the following reactions will be closely monitored:

- Acute hypersensitivity

Humans administered with foreign proteins are at risk of developing allergic reactions, including anaphylaxis. Patients can present with the following symptoms: itching, flushing, headache, nausea/vomiting, hypotension, urticaria, bronchospasm, or angioedema.

- Infections

Subjects treated with S95011 may be at an increased risk of infection. Administration of S95011 could be expected to result in immunomodulation with a decreased capacity to mount a response to novel immunogens, including those of bacterial, viral, fungal and parasitic origin when full receptor occupancy has been achieved.

- Cytokine release syndrome

No cytokine release has been observed in FIH study (IFN γ , IL12p70, IL4, IL5, IL6, IL8, TNF α). However, given the risk of cytokine release syndrome observed in certain therapeutic monoclonal antibodies, this event cannot be ruled out in patients treated with S95011.

- Vaccination

Vaccination of patients during treatment with S95011 and prior to clearance of S95011 is likely to result in non-protective vaccinal antibody titers due to the pharmacologic activity of the antibody.

- Immunogenicity

Extrapolation of immunogenicity risks from healthy subjects to pSS patients is unknown.

- Lymphopenia

No clinically significant lymphopenia has been observed neither in the phase 1 study nor in preclinical studies. However, due to S95011 mechanism of action, a possible lymphopenia cannot be ruled out.

The possible risks and their mitigations are presented in the table below.

Risks	Mitigations

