8.6. Definition of Adverse event of special interest

An adverse event of special interest (AEOSI) is one of scientific and medical interest or concern regarding the IMP for which recording rules, special documentation with detailed information such as hospital records is required. It may be a serious or non-serious AE that may require further investigation in order to characterize and understand.

AEOSI include:

- Allergic reaction grade 3 or higher according to CTCAE/v5.0 grading including infusion related reaction (Note: Humans administered foreign proteins are at risk of developing allergic reactions, including anaphylaxis).
- Cytokine release syndrome: No cytokine release has been observed in FIH study (IFN γ , IL12p70, IL4, IL5, IL6, IL8, TNF α), however, given the risk of cytokine release syndrome observed in certain therapeutic monoclonal antibodies, this event will be systematically collected and closely monitored in patients treated with S95011). In case of suspicion of cytokine release syndrome, a blood sample for cytokines assay will be performed and analysed locally.
- Infections grade 3 or higher according to CTCAE/v5.0 grading (Note: IL 7 receptor inhibition may induce immunomodulation, so patients should be monitored clinically for manifestations of infectious disease, and, if necessary, appropriately treated [e.g. with antibiotics]).
- Lymphopenia $<500 \times 10^6/L$ (grade 3 or higher according to CTCAE v5.0 Criteria)

No safety concern with S95011 (See Investigator's Brochure) has been identified in preclinical studies and phase I study.

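### The allergic-reaction AEOSI has no selection list titled for allergy; unless the infusion-reaction list is broader than its title, some grade 3+ allergic events may be left out of the AEOSI table

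*SAP*

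**What the plan says.** Protocol 8.6 gives the first AEOSI as "Allergic reaction grade 3 or higher according to CTCAE/v5.0 grading including infusion related reaction". Allergic reaction is the parent category there, and infusion related reaction falls within it.

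SAP 7.2.3.1 restates it as "Allergic reaction grade 3 or higher according to CTCAE/v5.0 grading (Note: Humans administered foreign proteins are at risk of developing allergic reactions", and the note goes on to name anaphylaxis. The words on infusion related reaction are not carried over. The other three AEOSI are cytokine release syndrome, infections of grade 3 or higher, and lymphopenia.

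The same SAP section then states "The lists of the considered ATC codes for AEOSI are the excel files" and names four:

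- "3736.0 PRE Infusion related reaction M251"
- "3847.0 Lymphopenia M250"
- "4314.0 Bacterial, viral, fungal, parasitic infections for 95011 M250"
- "4639.0 Cytokine release syndrome M250"

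SAP 4.4.1 plans a summary of AEOSI with counts of events and patients by system organ class and/or preferred term.

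**The concern.** The protocol's background section puts acute hypersensitivity first among the reactions to be closely monitored. It says that patients may present with "itching, flushing, headache, nausea/vomiting, hypotension, urticaria, bronchospasm, or angioedema". Several of these can be coded under their own term and not as an infusion reaction.

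The SAP describes only one way of picking events for the AEOSI table, the four lists. The list that evidently serves the allergic AEOSI is titled for one part of it. If the programmer selects by that list, and the list holds what its title says, a grade 3+ anaphylaxis or angioedema coded as such could meet the SAP's own AEOSI definition and yet be absent from the AEOSI table. That table is the only planned output that groups allergic events as one category.

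**Working it through.** There is no figure in the plan to reproduce, so the check sets definitions against lists.

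**Step 1: match each AEOSI in SAP 7.2.3.1 to a list by title.**

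| AEOSI | List by title | Match |
|---|---|---|
| Allergic reaction, grade 3+ | 3736.0, infusion related reaction | Part only |
| Cytokine release syndrome | 4639.0 | Yes |
| Infections, grade 3+ | 4314.0 | Yes |
| Lymphopenia | 3847.0 | Yes |

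Three of the four match. The fourth is covered only for infusion related reactions, which protocol 8.6 places inside the wider allergic category.

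**Step 2: look for another route into the table.** SAP 4.4.1 and 7.2.3.1 mention no e-CRF flag, no medical review and no reconciliation with notified events as a means of selecting AEOSI. SAP section 6, which records departures from the protocol's analyses, does not mention the allergic AEOSI or its lists.

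**Step 3: see where an unlisted event would still show.** SAP 4.4.1 plans tables of all TEAE, grade 3-4 TEAE, TEAE related to IMP, TEAE leading to IMP withdrawal, and SAE. A grade 3+ allergic event enters each of these where it meets the definition. Protocol 8.7 requires AEOSI, as defined in protocol 8.6, to reach the sponsor within 24 hours at the latest. Protocol 12.4 has the DSMB review events requiring immediate notification. None of these depends on the SAP lists.

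**Step 4: size per omitted patient.** The planned numbers are 30 on S95011 and 15 on placebo (protocol 10.2).

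- S95011: 1/30 = 0.033, or 3.3 percentage points.
- Placebo: 1/15 = 0.067, or 6.7 percentage points.

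These are the changes per omitted patient. The documents give no expected number of such patients.

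**Step 5: the label.** The SAP calls the AEOSI files lists of ATC codes. SAP 7.2.1.1.4 and 7.2.1.3 use ATC for the classification of treatments, and protocol 14.2 codes adverse events in MedDRA. The AEOSI files end in M250 or M251, while the drug lists end in DDB numbers. The phrase was therefore probably carried over from the drug sections, though that is an inference.

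**The case against.** The strongest reply is that everything turns on a file nobody outside the sponsor can see. Three lists pair off with three AEOSI, so 3736.0 is evidently the list assigned to the allergic AEOSI, and it may well hold anaphylaxis and hypersensitivity terms. If so, the defect is a narrow title and nothing is omitted. This stands. A reader might infer from the titles that allergic events would be missed; the documents do not support that, only that the SAP does not show they are covered.

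A reader might also infer that serious allergic events could escape safety reporting. They would not: Step 3 shows several other outputs, and expedited notification follows the protocol's definition, not the SAP's lists. In a trial of 45 planned patients, a grade 3+ allergic event would be visible in those outputs. No hypothesis test uses the AEOSI table.

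Three smaller inferences also go too far. The grade 3 threshold is not missing, because the SAP definitions of allergic reaction and of infections both state it. The dropped words on infusion related reaction have no shown effect on the table, because list 3736.0 targets those events by title. The ATC label is unlikely to mislead a programmer, because the files are titled with event terms.

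What the reply does not remove is that a stated selection rule, read as titled, is narrower than the definition it serves, and that nothing in the SAP closes the difference.

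**Conclusion.** The point holds as a possible gap in one descriptive safety table. By title, the selection list for the allergic AEOSI covers only infusion related reactions, whereas the AEOSI is any allergic reaction of grade 3 or higher. An event is left out only if three things are true together: list 3736.0 is no broader than its title, the event is grade 3 or higher, and it is coded under a term outside that list. The first cannot be checked from the documents. If it is false, what remains is a matter of titling and documentation.

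The consequence per event is modest in reach but not trivial in a small trial: 3.3 percentage points of the S95011 arm for each omitted patient, on a risk that the protocol lists first. Expedited reporting, the other adverse event tables and the primary analysis are unaffected. The point is worth correcting because the table exists to summarise such risks and the correction is cheap.

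**What to change.** - Add a MedDRA list of hypersensitivity and anaphylaxis terms for the allergic-reaction AEOSI, restricted to grade 3 or higher as the SAP definition already requires. If list 3736.0 already contains those terms, say so in SAP 7.2.3.1 instead.
- State that the AEOSI table will be cross-checked against events notified as AEOSI under protocol 8.7, with any difference explained.
- As editorial corrections, align the SAP definition with protocol 8.6 by restoring the reference to infusion related reaction, and describe the files as MedDRA term lists in place of ATC codes.

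The cost is at most one term list, one reconciliation and a few words in the SAP. No data collection changes.

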4.4.1. Adverse events

Definition:

- **Treatment Emergent Adverse Events (TEAE)** on the ASSE-W013 period are defined as all adverse events:

- Which occur between the infusion start date/time of the first IMP intake (included) and the date of W013 visit (included) or the last IMP intake date + 21 days (included) if the W013 visit has not been done

or

- Which occur before the infusion start date/time of the first IMP intake and which worsen (in terms of intensity) or become serious according to the investigator opinion between the infusion start date/time of the first IMP intake (included) and the date of W013 visit (included) or the last IMP intake date + 21 days (included) if the W013 visit has not been done.

Of note, in case of multiple information of the same event before the first IMP intake date, the information nearest to the first IMP intake date is taken into account.

- **Treatment Emergent Adverse Events (TEAE)** on the ASSE-W028 period are defined as all adverse events:

- Which occur between the infusion start date/time of the first IMP intake (included) and the last IMP intake date + 85 days (included),

or

- Which occur before the infusion start date/time of the first IMP intake and which worsen (in terms of intensity) or become serious according to the investigator opinion between the infusion start date/time of the first IMP intake date (included) and the last IMP intake date + 85 days (included).

Of note, in case of multiple information of the same event before the first IMP intake date, the information nearest to the first IMP intake date is taken into account.

Analysis:

Number of events, number and percentage of patients reporting at least one event, presented by primary system organ class, and/or preferred term (depending on the analysis), will be provided for:

- Serious adverse events (SAE) over the analysed period according to the investigator or sponsor opinion.
- Adverse events of special interest.
- Treatment Emergent Adverse Event (TEAE).
- TEAE leading to IMP withdrawal.
- TEAE requiring new treatment or increase of on-going treatment.
- TEAE requiring surgical or medical procedure.
- TEAE related to IMP.
- TEAE related to Pss.
- Serious TEAE.
- Serious TEAE related to IMP.
- TEAE of Grade 3-4 intensity.
- Non serious TEAE over the corresponding treatment period.

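### Partial dates of an adverse event's worsening or action taken have no floor at its own onset, so a higher grade or an IMP withdrawal can be dated before emergence and drop out of the safety tables

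*SAP*

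**What the plan says.** Table (7.2.3.1) 2 in SAP 7.2.3.1 governs the "substitution of missing or incomplete onset date, dates of modification of intensity, dates of action taken and/or dates of the six seriousness criteria". Apart from dates lacking only the time or minutes, it has three rules:

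- Day missing: "If same month and year as IMP intake date then: First IMP intake date and time + 1 min Else: 01/mmm/yyyy 00:00".
- Day and month missing: "If same year as IMP intake date then: First IMP intake date + 1 min Else: 01/JAN/yyyy 00:00".
- Date wholly missing: "First IMP intake date and time + 1 min".

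The same section sets the counting windows. For intensity, "the worst intensity from the day of emergence to the end of the studied period will be taken into account". For action taken, "all the actions taken recorded from the day of emergence to the end of the studied period will be taken into account". SAP 4.4.1 makes an event emergent in the main period by when it occurs: "Which occur between the infusion start date/time of the first IMP intake (included) and the date of W013 visit (included", with a fallback if W013 was not done. An event that starts on treatment therefore emerges at its own onset. The outputs listed in 4.4.1 include "TEAE leading to IMP withdrawal" and TEAEs of grade 3-4 intensity.

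Table (7.2.3.1) 3, for recovery dates, works differently. When the known month or year matches that of the event's last information date, it uses that last information date, which is a maximum that includes onset.

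**The concern.** Moving a partial onset date early is cautious, because it favours calling the event treatment-emergent. Moving a later date of the same event early does the opposite once it passes the event's own onset: the record leaves the window that starts at emergence. The event is then tabulated at its lower initial grade, or without the action that stopped the drug.

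The lines exposed are severity, grade 3-4 TEAEs and TEAEs leading to IMP withdrawal. They matter in a first study in pSS patients with 45 planned. The SAP expects partial dates here: section 7.1.2 omits substitution for IMP dates because those are complete, and nothing similar is said of AE dates.

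**Working it through.** The plan gives no figure to reproduce, so the check applies the rule as written. "IMP intake date" in the table's conditions is read as the first infusion, which is the milder reading. If any infusion counted, more partial dates would go back to the first one.

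**Worked example (assumed dates).** First infusion 10 January 2022. Onset 10 March at a low grade. Worsening or drug stop truly on 20 March.

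| What is known of the later date | Substituted date | On or after onset day? |
|---|---|---|
| Full date, time missing | 20 March | yes, counted |
| Month and year | 1 March | no, lost |
| Year only | 10 January + 1 min | no, lost |
| Nothing | 10 January + 1 min | no, lost |

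With the floor, max(substituted date, onset), each lost case becomes 10 March and is counted.

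**When the record is not lost (day missing).** With onset 25 March and the change in April, the substituted date is 1 April, after onset. With onset on 1 March and the change in March, it is 1 March, the onset day. If onset and change both lack the day, none is lost. For an event that began before treatment and worsened on it, none is lost, because the substituted worsening date is itself the emergence date.

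**How the condition depends on lag.** Enumeration over every first-infusion date in 2022, with complete onsets 1 to 90 days later and assumed lags from onset to change, gives the share of substituted dates falling before onset:

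| Lag (days) | Day missing | Day and month missing | Wholly missing |
|---|---|---|---|
| 0 | 97% | 100% | 100% |
| 3 | 87% | 99% | 100% |
| 7 | 74% | 98% | 100% |
| 14 | 51% | 96% | 100% |
| 28 | 5% | 92% | 100% |

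These shares are conditional on a partial later date with a complete on-treatment onset. They are not estimates of how often that happens.

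**Is there a floor elsewhere?** The default in SAP 7.1.3 applies only where no specific rule exists, and it also uses the first of the month. Table (7.2.3.1) 3 covers recovery only.

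**Size per patient.** 1/30 = 3.3 percentage points of the planned S95011 arm; 1/15 = 6.7 points of placebo. This assumes the patient has no other AE qualifying for the same line.

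**The case against.** The strongest reply is that such dates should be uncommon. Protocol 8.9.2.2 requires a new complete evaluation for any change in intensity or measures taken. Protocol 5.6.2 requires the date and reason of treatment discontinuation in the medical file and e-CRF. Protocol 14.2 provides queries and a blind review before each lock, and treatment visits are two to three weeks apart. All of this stands as to frequency. None of it changes what the table returns when a partial date remains.

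Three stronger readings are tempting, and the documents do not support them.

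- *Early substitution only ever removes events.* A missing floor can only lose records, but the table as a whole has mixed effects. With first infusion on 10 January, W013 falls 91 days later, on 11 April. A worsening truly on 28 April but recorded only as April becomes 1 April and enters the W013 window. The net direction is not established.
- *A month-only change date normally precedes onset.* In a month after that of the first infusion, 30 of 31 onset days are affected, but only if the change is in the onset month. The share falls to about half at a 14-day lag and 5% at 28 days. Likewise, a year-only date is not lost if the known year is later than that of onset.
- *Patients or outcomes disappear.* The TEAE stays, and seriousness stays because 7.2.3.1 accepts its criteria at any time. SAP 4.1.1 separately summarises withdrawal reasons overall and by visit. SAP 7.2.2.1 defines the discontinuation intercurrent events (IE1, IE3) without using these counting windows, so no effect on the efficacy estimand follows.

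**Conclusion.** The point holds as a defect in a stated rule, under conditions. The event must start on treatment, with onset known more precisely than the later change. The change date must lack at least the day, and its known part must not place it in a later month (or year) than onset. When these coincide, the substituted date can precede onset, and the worst-intensity or action-taken rule then excludes the record.

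The cost is a grade shown too low or an IMP-withdrawal flag missing, at 3.3 or 6.7 percentage points per affected patient on the planned arm sizes. The total cannot be sized, because the number of partial AE dates is not given; it may be small or nil. A reader should not infer that grade 3-4 or withdrawal counts are materially understated, only that the rule can understate them without any warning.

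**What to change.** Keep Table (7.2.3.1) 2 unchanged for onset dates. Add one sentence: for a partial or missing date of intensity modification, action taken or seriousness criterion, use the later of the date from the table and the onset date/time of that AE (itself substituted if partial), and never a date before the preceding recorded modification of the same AE.

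This brings the table into line with the principle in Table (7.2.3.1) 3. It costs one SAP sentence and one line of derivation code, and changes no date already on or after onset and any preceding modification. In particular, it leaves the 1 April example above as it is. Listing the affected records at blind review would show whether the point had any effect.
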